9. SOURCE DOCUMENTATION, STUDY MONITORING AND AUDITING

In order to ensure consistency across sites, study monitoring and auditing will be standardized and performed in accordance with the Sponsor's or delegated contract research organization's (CRO) standard operating procedures and applicable regulatory requirements (e.g., FDA, EMA, and ICH guidelines).

Prior to enrolment of the first study subject, Seqirus or delegate will train investigators and/or their study staff on the study protocol, all applicable study procedures, documentation practices and all electronic systems. CRFs supplied by the Sponsor or delegate must be completed for each enrolled subject (see [Section 8.3.1, All Enrolled Set for definition of enrolled subject](#)). Documentation of screened but not enrolled subjects must be maintained at the site and made available for review by the site monitor. Data and documents will be checked by the Sponsor and/or monitor.

9.1 Source Documentation

Prior to the start of the study, the site staff participating in the study conduct will be instructed on what documents will be required for review as source documents. The kinds of documents that will serve as source documents will be agreed between Sponsor or delegate and investigator and designees and specified in the SDA prior to subject enrolment.

In addition, source documentation **must** include all of the following: subject identification (on each page), eligibility and participation, proper informed consent procedures, dates of visits, adherence to protocol procedures, adequate reporting and follow-up of adverse events, documentation of prior/concomitant medication/vaccines, study vaccine receipt/dispensing/return records, study vaccine administration information, any data collected by a telephone conversation with the subject and/or parent(s)/legal guardian(s) and date of completion and reason.

The subject and/or parent(s)/legal guardian(s) must also allow access to the subject's medical records. Each subject and/or the parent(s)/legal guardian(s) must be informed of this prior to the start of the study and consent for access to medical records may be required in accordance with local regulations.

All safety data reported by subjects must be written down in source documents prior to entry of the data into the eCRFs. If there are multiple sources of information (e.g., Subject Diary, verbal report of the subject, telephone contact details, medical chart) supporting the diagnosis of an adverse event, these sources must be identified in the source documents, discrepancies between sources clarified, the ultimate diagnosis must be

justified and written in the source documents, and this diagnosis must be captured in the Adverse Event eCRF (AE eCRF).

9.2 Study Monitoring, Auditing and Source Data Verification

Prior to enrolment of the first study subject, Seqirus or its designee (e.g., a CRO) will develop a Clinical Monitoring Plan to specify how centralized and/or on-site monitoring, including clinical specimen reconciliation, will be performed for the study. Study progress will be monitored by Seqirus or its designee as frequently as necessary to ensure:

- that the rights and well-being of human subjects are protected,
- the reported study data are accurate, complete, and verifiable from the source documents and
- the conduct of the study is in compliance with the current approved protocol/amendment(s), GCP and applicable regulatory requirements.

Contact details for the Seqirus team or its designee involved in study monitoring will be provided to the investigator. Study data recorded on eCRFs will be verified by checking the eCRF entries against source documents in order to ensure data completeness and accuracy as required by study protocol.

Data verification may also be performed through a centralized review of data (e.g., checking for outliers or other anomalies). Additional documents such as the investigator site file, pharmacy records, and informed consent documentation must also be available for review if requested. Arrangements for monitoring visits will be made in advance in accordance with the monitoring plan, except in case of emergency.

The investigator and/or site staff must make source documents of subjects enrolled in this study available for inspection by Seqirus or its representative at the time of each monitoring visit and Sponsor audits, when applicable. These documents must also be available for inspection, verification and copying, as required by regulations, by officials of the regulatory health authorities (e.g., FDA, EMA and others) and/or ECs/IRBs. The investigator and study site staff must comply with applicable privacy, data protection and medical confidentiality laws for use and disclosure of information related to the study and enrolled subjects.

10. DATA MANAGEMENT

10.1 Data Entry and Management

In this study, all clinical data (including, but not limited to, AE/SAEs, concomitant medications, medical history, and physical assessments), safety data, and immunogenicity data will be entered onto electronic case report forms (eCRFs) in a timely fashion by the investigator and/or the investigator's dedicated site staff. Data entered onto eCRFs are stored on a secure website. The data collected on this secure website are assimilated into an electronic data capture (EDC) system, which is compliant with Title 21 Part 11 policies of the Code of Federal Regulations ([FDA 1997](#)). The data system includes password protection and internal quality checks. The EDC system will be designed and validated by the Sponsor prior to activation for data entry by sites. The investigator or designated delegate must review data entered and electronically sign the eCRFs to verify their accuracy.

Access to the EDC system for data entry or review will require training and distinct individual access code assignments to those site staff members who will be entering study data and those involved in study oversight who may review study data. Data are collected within the EDC system, to which the Sponsor and site monitors have exclusively "read only" access.

10.2 Data Clarification

As part of the conduct of the trial, the Sponsor or delegate may have questions about the data entered by the site, referred to as queries. The monitors and the Sponsor are the only parties that can generate a query. All corrections and clarifications will be entered into the EDC system and will be identified by the person entering the information, the reason for the change, as well as the time of the changes made. If changes are made to a previously and electronically signed CRF, the investigator must confirm and endorse the changes.

10.3 Data Protection

Seqirus and its delegate respects the subjects' rights to privacy and will ensure the confidentiality of their medical information in accordance with all applicable laws and regulations.

The Sponsor as Data Controller according to the European Directive on the protection of individuals with regard to the processing of personal data and on the free movement of such data ([95/46/EC](#)) confirms herewith compliance to Directive [95/46/EC](#) in all stages of Data Management.

11. RECORD RETENTION

Investigators must retain all study records required by Seqirus and by the applicable regulations in a secure and safe facility. The investigator must consult a Seqirus representative or delegate before disposal of any study records, and must notify the Sponsor of any change in the location, disposition, or custody of the study files. Essential documents must be retained for 15 years. “Essential documents” are defined as documents that individually and collectively permit evaluation of the conduct of a study and the quality of the data produced. These documents should be retained for a longer period, however, if required by the applicable national regulatory or institutional requirements.

These principles of record retention will also be applied to the storage of laboratory samples, provided that the integrity of the stored sample permits testing.

12. USE OF INFORMATION AND PUBLICATION

Seqirus assures that the key design elements of this protocol will be posted in a publicly accessible database such as clinicaltrials.gov, and in compliance with current regulations.

Seqirus also assures that key results of this clinical study will be posted in a publicly accessible database within the required time-frame from the end of study as defined in [section 3.9, End of Study](#).

In accordance with standard editorial, ethical practices and current guidelines of Good Publication Practice ([Graf 2009](#)), Seqirus will generally support publication of multicenter studies only in their entirety and not as individual center data. In this case, a coordinating investigator will be designated by mutual agreement prior to the start of the study. The coordinating investigator will also sign the clinical study report on behalf of the principal investigators ([CPMP/EWP/2747/00](#)). Authorship will be determined by mutual agreement and in line with International Committee of Medical Journal Editors authorship requirements. Any formal publication of the study in which contribution of Seqirus personnel exceeded that of conventional monitoring will be considered as a joint publication by the investigator and the appropriate Seqirus personnel.

Seqirus must be notified of any intent to publish data collected from the study and prior approval from Seqirus must be obtained prior to submission for publication.

13. ETHICAL CONSIDERATIONS

13.1 Regulatory and Ethical Compliance

The study will be conducted in compliance with the protocol, GCP and applicable regulatory requirement(s).

This clinical study was designed and shall be implemented and reported in accordance with the ICH Harmonized Tripartite Guidelines for Good Clinical Practice, with applicable local regulations including [European Directive 2001/20/EC](#), [US Code of Federal Regulations Title 21](#), and [Japanese Ministry of Health, Labor, and Welfare](#), Seqirus codes on protection of human rights, and with the ethical principles laid down in the Declaration of Helsinki ([European Council 2001](#), [US Code of Federal Regulations](#), [ICH 1997](#)).

13.2 Informed Consent Procedures

Eligible subjects may only be included in the study after providing written informed consent or assent, as described in [Section 5.1.1, Informed Consent/Assent](#). Before the start of the study, the investigator will have the informed consent and any other materials that will be provided to the subjects reviewed and approved by the IRB/EC. This review and approval will be documented and stored with other study documents. The investigator or designee must fully inform the subject/subject's parent(s)/legal guardian(s) of all pertinent aspects of the study. A copy of the written informed consent will be given to the subject or the designee. The subject/designee must be allowed ample time to ask about the details of the study and to make a decision as to whether or not to participate in the study. The subject (and/or subject's parent(s)/legal guardian(s)) **must** sign the consent form indicating their agreement to participate in the study before any study-related procedures are conducted. The informed consent process may be conducted up to 10 days prior to vaccination on day 1.

Prior to the start of the study, Seqirus or its delegate will provide to investigators a proposed informed consent form that complies with the ICH GCP guideline and regulatory requirements and is considered appropriate for this study. Any changes to the proposed consent form suggested by the investigator must be agreed to by Seqirus or its delegate before submission to the IRB/EC and a copy of the approved version must be provided to the Seqirus monitor after IRB/EC approval.

Women of childbearing potential should be informed that taking the study medication may involve unknown risks to the fetus if pregnancy were to occur during the study and agree that in order to participate in the study they must adhere to the contraception requirements indicated in the protocol for the duration of the study. If case of doubts on

the ability of a subject to adhere to these requirements, that subject should not be allowed in the study

In addition, the investigator or designee should explain pertinent aspects of the study in an age appropriate manner to pediatric subjects who are eligible for informed assent in accordance with local policies. The subject and parent(s)/legal guardian(s) must be allowed ample time to ask about the details of the study and to make a decision as to whether or not to participate in the study. The subject and parent(s)/legal guardian(s) must sign the consent/assent forms indicating their agreement to participate in the study before any study-related procedures are conducted. If the parent(s)/legal guardian(s) are required to sign the informed consent form but are unable to read and write, a witness must be present during the informed consent discussion and at the time of informed consent signature. Similarly, when the subject is required to sign the informed consent form, and is unable to read and write, a witness must be present during the informed consent discussion and at the time of informed consent signature.

13.3 Responsibilities of the Investigator and IRB/EC

The protocol and the proposed informed consent form must be reviewed and approved by a properly constituted IRB/EC before study start. Properly constituted IRB/EC is defined in ICH Guideline for Good Clinical Practice E6 (R1), Section 3 ([ICH 1997](#)). A signed and dated statement that the protocol and informed consent have been approved by the IRB/EC must be given to Seqirus before study initiation. Prior to study start and at any time the protocol is amended during study conduct, the investigator is required to sign a protocol signature page confirming his/her agreement to conduct the study in accordance with these documents and all of the instructions and procedures found in this protocol and to give access to all relevant data and records to Seqirus monitors, auditors, Seqirus Clinical Quality Assurance representatives, designated agents of Seqirus, IRBs/ECs, and regulatory authorities as required. If an inspection of the clinical site is requested by a regulatory authority, the investigator must inform Seqirus immediately that this request has been made.

The investigator also responsible for the following:

- Maintaining a list of appropriately qualified persons to whom the investigator has delegated significant study-related duties.
- Demonstrating the capability of recruiting the required number of suitable subjects within the recruitment period.
- Demonstrating sufficient time and staffing to properly conduct and complete the study within the agreed study period.

- Ensuring that all persons assisting with the study are adequately informed about the protocol, the investigational product(s), and their study-related duties and functions
- Ensuring that appropriately trained health care professionals are responsible for all study-related medical decisions and for ensuring appropriate medical care of subjects experiencing any adverse event related to the study.
- If permission to do so is given by the subject and/or parent(s)/legal guardian(s), ensuring that the subject's primary healthcare provider is informed of the subject's participation in the study.

The investigator should not implement any deviation from, or changes of the protocol without agreement by the Sponsor and prior review and documented approval/favorable opinion from the IRB/IEC of an amendment, except where necessary to eliminate an immediate hazard(s) to study subjects, or when the change(s) involves only logistical or administrative aspects of the study (e.g., change in monitor(s), change of telephone number(s)). In addition, the investigator, or person designated by the investigator, should document and explain any deviation from the approved protocol.

The investigator may implement a deviation from, or a change of, the protocol to eliminate an immediate hazard(s) to study subjects without prior IRB/IEC approval/favorable opinion. As soon as possible, the implemented deviation or change, the reasons for it, and, if appropriate, the proposed protocol amendment(s) should be submitted:

- (a) to the IRB/IEC for review and approval/favorable opinion,
- (b) to the Sponsor for agreement and, if required,
- (c) to the regulatory authority(ies).

13.4 Protocol Amendments

An amendment is a written description of change(s) to or formal clarification of a study protocol which may impact on the conduct of the clinical study, potential benefit of the clinical study, or may affect subject safety, including changes of study objectives, study design, subject population, sample sizes, study procedures, or significant administrative aspects. An administrative change of a study protocol is a minor correction or clarification that has no significant impact on the way the clinical study is to be conducted and no effect on subject safety (e.g., change of telephone number(s), logistical changes). Protocol amendments must be approved by Seqirus, health authorities where required, and the IRB/EC. In cases when the amendment is required in order to protect the subject safety, the amendment can be implemented prior to IRB/EC approval. Notwithstanding, the need for formal approval of a protocol amendment, the investigator is expected to take

any immediate action required for the safety of any subject included in this study, even if this action represents a deviation from the protocol. In such cases, Seqirus should be notified of this action, the IRB/EC at the study site, and, if required by local regulations, the relevant health authority) should be informed within 10 working days.

Men ACWY	Meningococcal (Groups A, C, Y, W-135) Conjugate Vaccine
MN	Microneutralization
NOCD	New Onset of Chronic Disease
NH	Northern Hemisphere
NP	Nasopharyngeal
PCR	Polymerase Chain Reaction
PH	Proportional Hazards
PPS	Per Protocol Set
QIVc	Cell-derived Quadrivalent Influenza Vaccine
QIV	Quadrivalent Influenza Vaccine
RT-PCR	Reverse Transcription Polymerase Chain Reaction
SAE	Serious Adverse Event
SAP	Statistical Analysis Plan
sBLA	Supplement Biologics License Application

SDA	Source Data Agreement
SH	Southern Hemisphere
SOC	System Organ Class
SUSAR	Suspected Unexpected Serious Adverse Reaction
WHO	World Health Organization

1. BACKGROUND AND RATIONALE

This document presents the statistical analysis plan (SAP) for Seqirus, Protocol No. V130_12: A Phase III/IV, Stratified, Randomized, Observer Blind, Multicenter Clinical Study to Evaluate the Efficacy, Safety and Immunogenicity of a Cell-Based Quadrivalent Subunit Influenza Virus Vaccine Compared to Non-Influenza Comparator Vaccine in Subjects ≥ 2 years to < 18 Years of Age.

It describes the data and variables to be summarized and analyzed, including specifics of the statistical analyses to be performed. This analysis plan is compliant with ICH Harmonized Tripartite Guideline, 5 February, 1998, *Statistical Principles for Clinical Trials, E9*²; World Health Organization, WHO Technical Report, Series No. 924. 2004, Annex 1: *Guidelines on Clinical Evaluation of Vaccines: Regulatory Expectations*.³; and FDA CBER Guidance for Industry, May 2007, *Clinical Data Needed to Support the Licensure of Seasonal Inactivated Influenza Vaccines*⁴.

The DMC analysis will be detailed in the Charter and follow definitions noted in this SAP.

The goal of the current randomized, observer-blind, controlled absolute efficacy study is to demonstrate that QIVc prevents influenza in pediatric subjects in subjects 2 to < 18 years of age, and obtained data will be used to support the licensure of QIVc for the prevention of seasonal influenza in pediatric subjects. Direct comparison with a non-influenza comparator vaccine, Menveo, (licensed for use in pediatric subjects) will enable an estimation of the absolute efficacy of QIVc in preventing influenza in pediatric subjects. A non-influenza vaccine comparator has recently been used to show efficacy of an egg-based quadrivalent influenza vaccine in the pediatric population (Jain et al. 2013). This approach is consistent with Center for Biologics Evaluation and Research (CBER) Guidance for the licensure of seasonal influenza vaccines.

For further details on the background and rationale of the study, please refer to [protocol version 5.0, dated 13 December 2018, sections 1.1 \(background\) and 1.2 \(rationale\)](#).

Any deviations from the current statistical plan and changes in the conduct or planned analysis will be described and justified in the final Clinical Study Report (CSR), whether written post interim or final analysis.

2. STUDY OBJECTIVES AND ENDPOINTS

2.1 Primary Objectives and Endpoint

2.1.1 Primary Efficacy Objective

The primary efficacy objective of the study is to demonstrate absolute vaccine efficacy of QIVc versus a non-influenza comparator determined by first occurrence RT-PCR or culture confirmed influenza, due to any influenza Type A and B strain in *subjects* ≥ 2 years to < 18 years of age.

In case of successful demonstration of the primary efficacy objective:

Co-Primary Efficacy Objective

The co-primary efficacy objective is to demonstrate absolute vaccine efficacy of QIVc versus a non-influenza comparator determined by first occurrence RT-PCR or culture confirmed influenza, due to any influenza Type A and B strain in *subjects* ≥ 3 years to < 18 years of age.

2.1.2 Primary and Co-Primary Endpoint

The primary and co-primary efficacy endpoint is the time from the last study vaccination to the onset of the first occurrence confirmed influenza by either RT-PCR-confirmed or culture-confirmed, due to any influenza Type A or B strain regardless of antigenic match to the strains selected for the seasonal vaccine, occurring > 14 days after the last vaccination and until the end of the influenza season.

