Subjects who show clinical signs of influenza (see ILI case definition) will have an unscheduled visit in order to have a nasopharyngeal (NP) swab (or oropharyngeal swab if collection of NP swab is not feasible) collected for evaluation of the presence of influenza virus, and a safety follow-up call 30 days after ILI onset to determine if subsequent medically-attended adverse events occurred and concomitant medication associated with these events were used. The NP swab should be collected as soon as possible, within 3 days, and up to 6 days following onset of protocol defined ILI symptoms. In case ILI symptoms are present during a scheduled clinic visit, then the NP swab may be collected at this visit. NP swabs will be evaluated by RT-PCR and culture at a central laboratory, followed by characterization of the influenza strains as “vaccine strains” versus other influenza strains. RT-PCR and culture confirmed influenza cases will be evaluated within specific timeframes of first and second study vaccination (i.e., starting 14 days after study vaccination for “previously vaccinated” subjects and starting 14 days after second study vaccination for “not previously vaccinated” subjects). The evaluation for RT-PCR and culture influenza cases will end at the end of influenza season.

Total length of subject participation is until 180 days after last vaccination, or until the end of influenza season, whichever is longer.

This study is planned for multiple influenza seasons. Laboratory confirmed influenza cases will be reviewed on a regular basis (blinded review). Following the end of the second influenza season, and after observing at least 50% of planned events meeting the co-primary endpoint, an interim analysis for efficacy and futility will be performed by a DMC.

If the number of influenza cases is less or equal to 190 (minimum number of cases to

indicate efficacy or futility), no interim analysis for efficacy and futility will be done and the study will be extended.

If the number of influenza cases is greater or equal to 191 but less than 381 an interim analysis for efficacy and futility with an appropriate adjustment of the type I error will be conducted by an DMC, to decide if study objectives have been reached or the study may be extended. The need for further interim analyses and further extensions will be assessed by the DMC. If it is determined that the study objectives have been reached, enrolment will be halted.

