4.2 Exclusion Criteria

Each subject must not have:

1. Individual with clinical signs of fever and/or an oral temperature of $\geq 100.4^{\circ}\text{F}$ (38.0°C) within three days prior to vaccination;
2. Individuals with a known history of any anaphylaxis, serious vaccine reactions or hypersensitivity to any of the vaccine components described in investigator brochure, or having any of the contraindications listed in the package insert of the comparator vaccine;
3. Individuals with history of Guillain-Barré syndrome or other demyelinating diseases such as encephalomyelitis and transverse myelitis;

4. Female subject “of childbearing potential¹”, sexually active, and not used any of the “acceptable contraceptive method²” for at least 2 months prior to study entry and intend to use until the end of subject participation;
5. Individual is pregnant or breast feeding female;
6. Individual and/or individual’ parent/guardians who are not able to comprehend or follow all required study procedures for the whole period of the study;
7. Individual has received prior Meningococcal ACWY vaccination that conflicts with national recommendations or local practices for timing of primary or booster vaccination
8. Individual has received influenza vaccination or has had documented influenza disease in the last 6 months;
9. Known or suspected congenital or acquired immunodeficiency; or receipt immunosuppressive therapy, such as anti-cancer chemotherapy or radiation therapy, within the preceding 6 months; or systemic corticosteroid therapy (prednisone or equivalent) at any dose for more than 2 consecutive weeks (14 days) within the past 3months. Topical, inhaled and intranasal corticosteroids are permitted. Intermittent use (one dose in 30 days) of intra-articular corticosteroids is also permitted;
10. Administration of immunoglobulin and/or any blood products within the 3 months preceding vaccination, or planned administration during the study;
11. Individual has participated in any clinical trial with another investigational product 30 days prior to first study visit or intent to participate in another clinical study at any time during the conduct of this study. Concomitant participation in an observational study (not involving drugs, vaccines, or medical devices) is acceptable;

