4.4 Criteria for Repeat Vaccination in the Study

Prior to receipt of second study vaccination (“not previously vaccinated” subjects), subjects must be evaluated to confirm that they are eligible for subsequent vaccination. If subjects meet any of the original exclusion criteria (except for those listed under [Section 4.3](#)) or the criteria listed below, they should not receive additional vaccinations.

- Subjects who experience any SAE judged to be related to study vaccine including hypersensitivity reactions.
- Subjects who develop any new condition which, in the opinion of the investigator, may pose additional risk to the subject if he/she continues to participate in the study.

Subjects who meet any of these criteria must not receive further study vaccinations. However, these subjects should be encouraged to continue study participation, as discussed in [Section 3.6](#).

There are also circumstances under which repeat vaccination is a contraindication in this study. These circumstances include anaphylaxis or severe hypersensitivity reactions following vaccination. If these reactions are to occur, the subject must not receive additional vaccinations but is encouraged to continue in study participation.

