7.3 Full Analysis Set (FAS), Efficacy/Immunogenicity Set

FAS, Efficacy: All subjects in the All Enrolled Set who received at least one dose of study vaccine and are evaluated for efficacy from 14 days after the last vaccination.

FAS, Immunogenicity: All subjects in the All Enrolled Set who received at least one dose of study vaccine and provide evaluable serum samples at both baseline and after the last vaccination.

Last vaccination is at Visit 2 for "previously vaccinated" subjects and at Visit 3 for "not previously vaccinated" subjects.

FAS will also be defined by time point and objective:

- *FAS-Eff1* will include all subjects ≥ 2 years to < 18 years of age who received at least one dose of study vaccine and are evaluated for efficacy from 14 days after the last vaccination (primary objective).
- *FAS-Eff2* will include all subjects ≥ 3 years to < 18 years of age who received at least one dose of study vaccine and are evaluated for efficacy from 14 days after the last vaccination (Co-primary objective).
- *FAS-HII* will include all subjects ≥ 2 years to < 9 years of age who received at least one dose of study vaccine and provide evaluable serum samples for HI analysis at both baseline and after the last vaccination (secondary objective).
- *FAS-MNI* will include all subjects ≥ 2 years to < 9 years of age who received at least one dose of study vaccine and provide evaluable serum samples for MN analysis at both baseline and after the last vaccination (exploratory objective).

In case of vaccination error, subjects in the FAS will be analyzed “as randomized” (i.e. according to the vaccine a subject was designated to receive, which may be different from the vaccine the subject actually received).

If a subject is unblinded during the study, he/she will be included in the FAS.

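### The documents give conflicting time zeros for a two-dose-stratum child who never receives dose 2, and under the natural SAP reading the outcome itself can decide which applies

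*SAP*

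**What the plan says.** **Endpoint.** SAP 2.1.2 defines it as follows: "The primary and co-primary efficacy endpoint is the time from the last study vaccination to the onset of the first occurrence confirmed influenza". Cases count if they occur more than "14 days after the last vaccination and until the end of the influenza season". Protocol 8.1.1.2 agrees. SAP 8.6 (derived variables) contains no derivation of the event time.

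**Primary analysis set.** SAP 7.3 admits children "who received at least one dose of study vaccine and are evaluated for efficacy from 14 days after the last vaccination". SAP 11.1 bases the primary and co-primary analyses on this set (FAS) and repeats them on the per-protocol set (PPS). One dose is enough for entry, so a two-dose-stratum child who stops after dose 1 is in the primary analysis.

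**Other anchors.** Protocol 3.1 evaluates cases in the not-previously-vaccinated stratum "starting 14 days after second study vaccination". SAP 7.3 adds "Last vaccination is at Visit 2 for" previously vaccinated children, and at Visit 3 for the others. Protocol Tables 3 and 5 show these as the Day 22 and Day 50 visits, with no vaccination at either.

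**Receipt of dose 2.** Protocol 4.4 re-checks eligibility before dose 2. The rule opens "If subjects meet any of the original exclusion criteria (except for those listed under" Section 4.3, and its result is no further vaccination. Protocol 5.2.2 repeats it. Exclusion criterion 8 in Protocol 4.2 reads "Individual has received influenza vaccination or has had documented influenza disease in the last 6 months". Children who stop are encouraged to stay in the study. Swabbing for influenza-like illness runs from Day 1 (Protocol 3.5), and swabs are tested in batches (Protocol 3.6).

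**The concern.** The primary endpoint has to be programmed one way before unblinding, and for an incomplete two-dose course the text supports more than one way.

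The reading that SAP 2.1.2 and 7.3 most naturally support is also the awkward one. Take two children in the same arm and stratum, each with influenza onset on Day 20. In the first, the illness is documented before Day 29 and dose 2 is withheld. Last vaccination is then Day 1, and the Day 20 illness is a primary case. In the second, the result is not yet known and dose 2 is given. Last vaccination is then Day 29, and the same illness falls before time zero and is not counted. Time zero and case status would both depend on an event after randomisation that the outcome and laboratory turnaround can determine.

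The illnesses admitted in this way follow one dose of a planned two-dose course, so they mix one-dose protection into the estimate. If one dose protects partly, fewer QIVc than comparator children would be moved to the Day 1 clock.

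**Working it through.** **1. The plan's own figures.** Co-primary objective: true VE 50%, margin 30%, 1:1 allocation, two-sided 5%, 90% power (SAP 5). Schoenfeld events = 4(1.960 + 1.282)² / [ln(0.50/0.70)]² = 372, against 381 stated; power at 381 events is 90.7%. Primary objective: 4(1.960 + 1.282)² / [ln(0.55/0.80)]² = 300, against 298 stated. Evaluable children: 381 / 0.06 = 6,350, as stated. Enrolled: 6,350 / 0.90 = 7,056, as stated. The event targets are sound, and this point does not change them.

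**2. When the window opens.** More than 14 days after a dose means dose day + 15.

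| Reading, for a two-dose-stratum child without dose 2 | Window opens |
|---|---|
| Last dose received (natural reading of SAP 2.1.2 and 7.3) | Day 1 + 15 = Day 16 |
| Second vaccination (Protocol 3.1, literal) | no window |
| Visit 3 (SAP 7.3, literal) | Day 50 + 15 = Day 65 |
| For comparison: a child given dose 2 on Day 29 | Day 29 + 15 = Day 44 |

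The ±3-day visit window for dose 2 makes the last row Day 41 to Day 47. SAP 7.3 and Protocol 3.1 start at 14 days, not after more than 14, which moves each opening one day earlier (Day 15 and Day 43).

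**3. Size under the last-dose-received reading.** Inputs from the documents: 1,022 to 1,430 two-dose children per arm (2,044 to 2,860 of 7,692, or 27% to 37%), comparator attack rate 8%, dropout 10%. At VE 50%, the 381 cases split 254 comparator and 127 QIVc. Assumptions not in the documents: season length L, the share s of Day 16 to 29 influenza documented before dose 2 (taken as equal in both arms), one-dose VE v, and a constant hazard.

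Extra comparator cases: c = n × 0.9 × (1 − exp(−14h)) × s, with h = −ln(0.92)/L. Extra QIVc cases q use h(1 − v). Then VE = 1 − (127 + q)/(254 + c).

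| s | v | L (days) | c | VE |
|---|---|---|---|---|
| 10% to 25% | 0 | 120 to 240 | 0.4 to 3.1 | 49.9% to 49.4% |
| 100% | 0 | 120 to 240 | 4.5 to 12.5 | 49.1% to 47.7% |
| any | 50% | 120 to 240 | as above | 50.0% |

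For example, with n = 1,430, L = 120, s = 100% and v = 0, c = q = 12.5 and VE = 1 − 139.5/266.5 = 47.7%.

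A harsher case uses a 90-day season without dropout: c = 1,430 × 0.08 × 14/90 = 17.8. With s = 100% and v = 0, VE = 1 − 144.8/271.8 = 46.7%. With s = 25%, c = q = 4.45 and VE = 1 − 131.45/258.45 = 49.1%.

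**4. Cross-check.** A Cox simulation (1,430 two-dose children per arm, all Day 16 to 29 influenza documented, no one-dose protection, 180-day season) gave mean VE of 47.9% with the last-dose-received clock and 49.5% counting only after dose 2. Both come from the same simulated data, with Monte Carlo standard errors of about 0.7 points each. The gap agrees with the arithmetic.

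**5. Stopping unrelated to influenza.** If 1% to 10% of the stratum misses dose 2 for other reasons, the extra 28 days (Day 16 to Day 43) add about 0.1 to 2.8 comparator cases.

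**The case against.** A reader might infer that the SAP lays down the last dose received as time zero. It does not: no passage says received. Protocol 3.1 names the second vaccination, and the Visit 2/Visit 3 sentence in SAP 7.3 assigns last vaccination by stratum, not by receipt. That sentence follows the immunogenicity definition and may belong to it. What stands is a conflict between passages, with last dose received as the natural reading of the SAP.

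A reader might also infer that every child with documented influenza between doses is refused dose 2. That cannot be taken as certain. Criterion 8 also names influenza vaccination in the last 6 months. Re-applied word for word on Day 29, it would stop every QIVc child from receiving the second dose that Protocol 3.1 schedules. The criterion and its re-application have to be reconciled before anyone can say how often dose 2 would be withheld for influenza.

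Early documentation is also doubtful. Testing is central and batched, swabs may be taken up to 6 days after onset, and no passage was found that returns results to sites by Day 29. Full documentation is therefore an upper bound.

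Finally, the rule is the same in both blinded arms, the scenarios only lower VE, and the PPS repeat removes one-dose children of this stratum. All of this stands and limits the size. The PPS is only a partial check, because it is itself selected after randomisation and is not the primary set. None of it supplies the missing time zero.

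**Conclusion.** The point holds as a conflict that should be resolved before unblinding. For a two-dose-stratum child without dose 2, the literal readings give a window from about Day 16, no window, or a window tied to a visit without vaccination. The natural SAP reading lets the outcome influence time zero.

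The likely effect is under 1 VE point: from 50% to no lower than about 49.4% at 10% to 25% documentation with seasons of 120 to 240 days and 10% dropout, or 49.1% for a 90-day season without dropout. If all such illness were documented and one dose gave no protection, the low end is about 46.7% to 47.7%. If one-dose VE is 50%, nothing moves. These figures rest on assumed season length, documented share and one-dose VE, none of which the documents give.

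It would go too far to say that the success criteria are at risk or that a false positive becomes more likely. In the scenarios examined VE falls or stays the same, and even the lowest estimate stays well above the 30% margin. The reason to act is that the primary case definition should have one meaning that does not depend on the outcome.

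**What to change.** In Protocol 3.1 and 8.1.1.2 and SAP 2.1.2, 7.3 and 11.1:

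- Set time zero by randomised stratum, in both arms, whether or not dose 2 is given: Day 1 for the one-dose strata and scheduled Day 29 for the two-dose stratum. Count cases more than 14 days after that date for every FAS child.
- If the actual dose-2 date is kept for children who receive it, use scheduled Day 29 only for those who do not. Acknowledge that postponement for fever or active infection (Protocol 5.2.2) can still let illness shift the date.
- State that influenza before the window opens is handled in the same way whether or not dose 2 was given, including what it means for first occurrence.
- Keep the last-dose-received clock as a sensitivity analysis.
- Correct the Visit 2/Visit 3 sentence in SAP 7.3, and use one wording for the 14-day rule.

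Separately, the sponsor must reconcile exclusion criterion 8 (Protocol 4.2) with its re-application before dose 2 (Protocol 4.4 and 5.2.2). This review takes no position on which clinical rule should apply.

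The cost is wording in both documents and one derived date. A few early cases in one-dose children leave the primary analysis. With a fixed Day 29, a child given dose 2 at the end of its window (Day 32) has cases counted from Day 44, which is 12 days after that dose.
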